5.1. Study design:⁸

Our community partners are two federally-qualified health centers (FQHC). FQHC #1 is located in the Tacoma area in Washington and the FQHC #2 is located in the San Fernando/Santa Clarita areas in Los Angeles, CA. FQHC #1 has 4 clinics participating in the study and FQHC #2 has 6 clinics participating in the study. The total number of clinics participating in the study is 10. The cluster randomization was conducted at the end of 2017 by the study statistician. The clinics were placed in blocks by FQHC, location and size and the assignment to control or intervention was done using a computer-generated random allocation. Below are the cluster-randomized assignments, stratified by block and clinic size:

Block	FQHC #1	Assignment
1	Eastside Lakewood	Intervention Control
2	Parkland Spanaway	Control Intervention

Block	FQHC #2	Assignment
1	Canoga Park Van Nuys	Control Intervention
2	Pacoima San Fernando	Intervention Control
3	Santa Clarita Valencia	Intervention Control

The five clinics randomized to intervention will implement the newly adapted model of well child check-up visits for children ages 0-3. The five clinics randomized to control will continue to use the same services that the clinics provide--their usual check-up visit as their typical clinician-led visit (well-visit time slots vary by practice).

Parent/legal guardians will receive the same services offered by these clinics for their child's health care whether they participate in this study or not.

Components of the newly designed model of WCC:

The PARENT intervention was adapted during the Project Working Group meetings in partnership with the two FQHCs (Phase 1: IRB ID: STUDY00000413).

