10.3. Number of screened subjects versus the actual number enrolled in the research:³¹

2 to 1. In other words, we will expect to screen doubled the number of actual people enrolled in the study

10.4. Power analysis:

The power calculation is based on WCC quality (anticipatory guidance) and ED visits (2 or more), with a 1:1 randomization of 10 sites into the intervention and control groups. We use the mean and standard deviation (SD) of anticipatory guidance and the rates of 2 or more ED visits as observed in our pilot RCT. For anticipatory guidance, we use the larger SD from the two groups to have a conservative power estimation for this variable. The calculation assumes an intra-class correlation of 0.01 based on previous delivery systems design cluster RCTs among similar populations^{81, 82} and the fact that the data analysis will be adjusted for important baseline covariates when comparing the intervention versus control groups⁸³. A 20% dropout rate is assumed at the patient level. Two-sided tests are used with a type I error rate of 0.05. With an N of 75 per site, we will have at least 80% power to detect the intervention effect for both anticipatory guidance and ED visits. After accommodating a 20% dropout rate at the patient level, the N per site is 94, or a total sample of 940 participants.

11. Withdrawal of Subjects

11.1. Anticipated circumstances under which subjects will be withdrawn from the research without their consent:

Subjects can choose whether to be in this study or not. If they agree to participate, they may withdraw their consent at any time without impacting their care. For this study, we do not anticipate the need to withdraw subject due to investigator judgement.

11.2. Procedures for orderly termination:

N/A

11.3. Procedures that will be followed when subjects withdraw from the research, including partial withdrawal from procedures with continued data collection and withdrawal from data/specimen banking:

Data collected on any withdrawn subjects will be removed from the analysis

12. Risks to Subjects**12.1. Reasonably foreseeable risks to subjects (include each study population, each arm, and optional procedures):**

There is a risk that confidentiality or privacy could be breached and people could find out if someone was in the study.

12.2. Procedures with unforeseeable risks:

N/A

12.3. Procedures with risks to an embryo or fetus should the subject be or become pregnant:

N/A

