the fact that randomization is done at the clinic level. The outcome may be subject to transformation prior to fitting the model if non-normality is observed. The analysis will include intervention status as the main independent variable, adjusted for baseline covariates and other confounding factors. We will also test possible interaction effects between intervention and these covariates. All other outcome variables to measure experiences of care and receipt of other nationally-recommended WCC services are regarded as secondary. Each outcome will be analyzed using linear or generalized linear mixed effects models depending upon data distributions, with a similar setting as described above for anticipatory guidance.

Specific Aim 2a: Intervention effects on healthcare utilization (ER visits, hospitalizations, urgent care visits, regional center/early intervention, maternal mental health, support groups (e.g., breastfeeding, parenting classes), dentist, case management/social services) will be assessed using generalized linear mixed effects models for binary or count data with a similar setup as outlined for Aim 1. The model will include random effects to capture data clustering within clinic and the primary independent variable is intervention status. The analysis will be adjusted for any baseline child, parent, or household characteristics that are significantly different between control and intervention groups. We will also test interaction effects between intervention and the covariates.

Specific Aim 2b: Cost/cost-offset Analysis. We will conduct our analysis from the perspectives of the “social planner”⁸⁰ and of the payer (e.g., health plan or medical group), and consider intervention costs (direct and indirect) and cost offsets.

Specific Aim 4: We will utilize the same approach as described for Specific Aims 1 and 2a; i.e., linear or generalized linear mixed effects models, depending on the distribution of the outcome variables.

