17.3. Types of communications that will be submitted to the IRB for review:³⁸

A direct message script will be submitted for review. This script shows the communication will be limited to scheduling and that participants will be encouraged to call the study team to discuss details and/or ask questions.

17.4. If user-generated content will be active, how it will be monitored and what actions will be taken to ensure subject safety and study integrity:

N/A

18. Research Related Injury³⁹**18.1. Available compensation in the event of research related injury:**

The study does not involve more than minimal risk to subjects

19. Recruitment Methods⁴⁰**19.1. When, where, and how potential subjects will be recruited:**

On-site recruitment:

Parents/legal guardians checking in for a newborn through 12 month visit will be approached by front desk staff. Those who agree will be approached while waiting for their WCC visit. Clinics will have flyers on display about the study as an additional method for alerting parents to the possibility of being approached by research staff. For those approached in clinic, study staff will explain the study, screen for eligibility, provide the consent form, and obtain consent. When possible, parents/legal guardians will be given the opportunity to discuss the study in a private room.

Off-site recruitment:

- **Method 1: When research staff are limited from recruitment on-site:** clinic sites will be informed of pre-screened visits that are anticipated to be eligible for enrollment. Clinic staff will be able to give parent/legal guardians a copy of the consent form/information sheet prior to research staff contacting them. Parent/legal guardians will have the option to decline a call from research staff. Study staff (who have access to the clinic WCC visit schedule and that have received training to use the clinic's EHR) will call families to explain the study, screen for eligibility, and obtain verbal consent over the phone and document the consent process by entering the date and time in RedCap.

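### Aim 2a, which covers the powered ED outcome, chooses covariates by a baseline significance screen, so it selects on imbalance rather than prognosis and leaves the ED model partly data-driven

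*Combined protocol and SAP*

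**What the plan says.** All references are to the combined protocol and SAP.

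- **Section 14.1, Specific Aim 2a** covers healthcare utilization, with ER visits listed first. Its covariate sentence reads: "The analysis will be adjusted for any baseline child, parent, or household characteristics that are significantly different between control and intervention groups". No covariate, baseline test or separate screening level is named; the only level in section 14.1 is the general two-sided 0.05. The same paragraph describes the models as built "with a similar setup as outlined for Aim 1", and it ends: "We will also test interaction effects between intervention and the covariates".
- **Section 14.1, Specific Aim 1** has no screen. Its model is "adjusted for baseline covariates and other confounding factors", again with none named.
- **Section 14.1, Specific Aim 4** points to Aims 1 and 2a together and does not say which covariate rule applies.
- **Section 10.4 (power analysis)** powers the trial on anticipatory guidance and on two or more ED visits. It supports the ICC of 0.01 by earlier trials and by "the fact that the data analysis will be adjusted for important baseline covariates when comparing the intervention versus control" groups.
- **Section 5.1**: "The cluster randomization was conducted at the end of 2017 by the study statistician". "The clinics were placed in blocks by FQHC, location and size".

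**The concern.** A significance test at baseline measures how far the arms differ on a variable. It says nothing about whether that variable predicts ED use. A strong predictor that happens to be balanced can be left out, and a variable unrelated to ED use can be put in.

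Three things follow. The ED model is not fully fixed until the baseline data have been examined. The adjustment for important covariates that section 10.4 relies on is not guaranteed by Aim 2a's own sentence. And because interactions are tested with whichever covariates are in the model, the screen also influences which effect modifiers are examined. At stake are precision and the ability of another analyst to reproduce the model from the plan.

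**Working it through.** **1. The plan's own figures.** Evaluable N is 75 per clinic with 20% dropout (section 10.4): 75 / 0.80 = 93.75, rounded up to 94; 94 × 10 = 940. This reproduces. The stated 80% power cannot be reproduced, because the pilot mean, SD and ED rates are not given.

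**2. A working effect size.** Design effect = 1 + (75 − 1) × 0.01 = 1.74. Effective N per arm = 375 / 1.74 = 215.5. Detectable difference at 80% power (normal approximation) = (1.960 + 0.842) × √(2 / 215.5) = 0.27 SD. For a binary outcome the same effective N detects, for example, 20% v 10.3% (the 20% is assumed). With a clinic-level t test on 8 df, noncentrality 0.27 / √(2 / 215.5) = 2.80 gives power of about 0.69. The continuous comparisons below start near that value; only differences between analyses matter here.

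**3. How often chance alone selects a covariate.** Suppose the screen ignores clinic, the covariate has ICC ρ, and the two-clinic blocks explain a share s of its between-clinic variance. The variance inflation is D = 1 + (94(1 − s) − 1)ρ, and the real level of a nominal 5% test is 2[1 − Φ(1.96 / √D)].

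| s | ρ = 0.01 | ρ = 0.02 | ρ = 0.05 |
|---|---|---|---|
| 0 | D 1.93, 15.8% | D 2.86, 24.6% | D 5.65, 41.0% |
| 0.5 | D 1.46, 10.5% | D 1.92, 15.7% | D 3.30, 28.1% |

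A clinic-level test (8 df) selects in about 5% of simulated trials at s = 0 and in 2% to 3% at s = 0.5. Either way, a balanced prognostic covariate is usually left out.

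**4. Power lost if the screen replaces Aim 1's covariates.** Simulation with ten clinics in five pairs, effect 0.27 SD, residual ICC 0.01 and 8,000 trials per cell. Entries are power with the covariate fixed in advance v screened (clinic ignored), for ρ = 0.01, 0.02, 0.05.

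| Correlation with outcome | s | ρ = 0.01 | ρ = 0.02 | ρ = 0.05 |
|---|---|---|---|---|
| 0.1 | 0 | 0.698 v 0.695 | 0.690 v 0.687 | 0.681 v 0.678 |
| 0.1 | 0.5 | 0.712 v 0.707 | 0.710 v 0.703 | 0.709 v 0.702 |
| 0.3 | 0 | 0.727 v 0.697 | 0.724 v 0.686 | 0.723 v 0.667 |
| 0.3 | 0.5 | 0.742 v 0.711 | 0.744 v 0.700 | 0.749 v 0.678 |

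The losses are 0.3 to 0.7 points at correlation 0.1 and 3.0 to 7.1 points at 0.3. With s = 0.8 the loss at 0.3 is 4 to 8 points.

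A clinic-level screen loses as much or more (3 to 8 points at 0.3), because it seldom selects anything and so comes close to no adjustment. A smaller run (4,000 trials, no blocks, slope 0.3) shows that limit: fixed v unadjusted was 0.688 v 0.654 at ρ = 0.01 and 0.693 v 0.593 at ρ = 0.05, so the ceiling is about 3 to 10 points.

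A logistic mixed model (20% v 10.3%, 8 df, clinic-ignoring screen, 1,500 trials per cell) loses under 1 point at an odds ratio of 1.25 per SD, about 1 to 3 at 2, and 4 to 8 at 3. The Monte Carlo standard error is √(0.8 × 0.2 / 1,500), about 1 point per power figure, so the smaller losses are of that order.

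**5. Power lost if the screen only adds to Aim 1's covariates.** One covariate (correlation 0.3) is always in and a second is screened; 6,000 trials. Entries are both fixed v additive screen.

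- Second at 0.1: 0.740 v 0.737, 0.736 v 0.733, 0.754 v 0.750, 0.749 v 0.742 (0.3 to 0.7 points).
- Second at 0.3: 0.770 v 0.734, 0.775 v 0.715, 0.801 v 0.770, 0.791 v 0.718 (3.1 to 7.3 points).

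If every important covariate is already in Aim 1's list, there is nothing to lose.

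**6. Type I error.** In 11 null settings of the logistic model with 8 df, the rule rejected in 1.3% to 5.3% of trials, and with either reference distribution never more than 0.3 points above no adjustment.

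**7. If a real baseline difference exists.** With a covariate of correlation 0.3, ρ = 0.01, s = 0.5 and a clinic-ignoring screen, a 0.1 SD difference gives bias of 0.029 SD unadjusted and 0.009 SD under the rule. A 0.2 SD difference gives 0.059 and 0.004 SD. The rule removes 1 − 0.009 / 0.029 = 69% and 1 − 0.004 / 0.059 = 93%. A clinic-level screen flags such differences less often and so removes less.

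**The case against.** **The screen may only add terms.** Aim 2a says it follows Aim 1's set-up, and section 10.4 commits to adjusting for important covariates. Read together, the screen may supplement a prognostic set rather than replace it. This stands as a possible reading. A reader might infer from the quoted sentence that Aim 2a drops Aim 1's covariates altogether; the documents do not settle that. But neither aim names a covariate, so the ED model stays partly data-driven on both readings.

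**The harm is modest and conditional.** This also stands. The documents do not show how strong the available covariates are, and weak ones make the loss negligible. A reader might infer that the screen produces false-positive findings, or that the sample of 940 is wrong; step 6 does not support the first, and nothing in the sample size depends on the screen. The argument that the harm needs a test ignoring clinic fails: a clinic-level screen costs as much or more.

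**Imbalance here may be real.** Families are recruited after allocation ("Parents/legal guardians checking in for a newborn through 12 month visit will be approached by front desk staff"), so baseline differences need not be chance, and adjusting for them has a purpose. The screen, if it ignores clinic, removes much of the bias in step 7, whereas a fixed list that omits such a covariate removes none of it from the main estimate. This stands, and the fix must provide for it.

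**Conclusion.** The point holds as one of specification and efficiency, and it should be corrected before outcome data are seen. Aim 2a states a rule that selects on observed imbalance, for a section of the plan that contains a powered outcome, while the power section relies on adjustment for important covariates that the rule does not secure.

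Under the assumed inputs the cost is about 1 power point or less for a covariate correlated 0.1 with outcome and about 3 to 8 points at 0.3. It approaches 10 only if the screen is clinic-level and the covariate is strongly clustered (ICC 0.05). Under the additive reading it is confined to predictors outside Aim 1's list and is nil if that list is complete. Validity is not threatened: type I error is not inflated, and the rule does no worse than no adjustment, within simulation error.

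The wording of the plan is certain. The size is not, because covariate strength, covariate ICC, block share and the ED rates are all assumptions. If the covariates prove weak, the gain is a fixed and reproducible model rather than power.

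**What to change.** Replace the significance screen in Aim 2a with one short list of baseline covariates chosen for expected prognostic value, not alterable by PARENT, and fixed before outcome data are seen. Candidates are infant age at enrolment and primary language (both on the clinic schedule, section 19.4) and demographics from the baseline survey (section 5.2). Use the same list for Aims 1, 2a and 4, and name from it the interactions to be tested. Describe baseline differences without testing them.

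Because families are recruited after clinics were allocated, keep a pre-specified sensitivity analysis that also adjusts for further baseline characteristics, including any that appear imbalanced.

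The cost is SAP wording, a check that the chosen variables were collected (the survey instruments are not reproduced in the documents), and one extra analysis. The target of 940 is unchanged. The downside is that an imbalanced covariate left off the list is corrected only in the sensitivity analysis, so the list deserves care.

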14.2. Quality control procedures for collected data:³³

The study team member who collected the data will enter the data into the study database and another team member will be validating the data entered.

15. Confidentiality³⁴

15.1. Procedures to secure the data and/or specimens during storage, use, and transmission:

All electronically maintained data will exist on encrypted devices and secure databases.

15.2. Location where the data and/or specimens will be stored:

Parent/Child participant data will be entered directly into a redcap database on password-protected laptops and smart tablets. Data initially collected on hard copy will be transferred to the secure, database. Hard copy documents will be kept in locked cabinets in a locked office. Identifiable information, such as consent forms, will be kept separately from data collection forms to ensure the de-identification of the data. Hard copy documents that are collected from clinics and transported to study offices will be kept in secure document holders to protect against breeches of confidentiality.

15.3. Length of time data and/or specimens will be stored:

5 years

15.4. Individuals with access to data and/or specimens:

Only relevant research staff will have access to the data.

15.5. Process for the transmission of data and/or specimens outside Seattle Children's:

15.5.1. List of data and/or specimens that will be transmitted:

Only de-identified data for purposes of data analysis

15.5.2. Individual(s) who will transmit data:

Only the PI, project manager, or project CRA

16. Provisions to Monitor Data to Ensure the Safety of Subjects³⁵**16.1. Plan to periodically evaluate the data collected regarding both harms and benefits to determine whether subjects remain safe.³⁶**

Research does not involve greater than minimal risk

16.2. Data reviewed to ensure safety of subjects:

N/A

16.3. Safety information collection procedures:

N/A

16.4. Frequency of cumulative data review:

N/A

16.5. Conditions that trigger an immediate suspension of the research:

N/A

17. Use of Social Media**17.1. Types of social media to be used and how:**

Twitter, Instagram and Facebook will be used. The only features of these social media platforms that will be used will direct messaging.

17.2. Measures in place to protect the privacy or confidentiality of subjects:³⁷

The study social media accounts will never “friend”, follow or engage in any way with participants’ social media pages. The only interaction or engagement will be via direct message. We will not search for individuals on social media and will only direct message those who provide us with permission to do so as well as their specific profile name.

Additionally, the study social media accounts will not be public to avoid any possibility of public interactions that could reveal identities of potential participants to each other.

17.3. Types of communications that will be submitted to the IRB for review:³⁸

A direct message script will be submitted for review. This script shows the communication will be limited to scheduling and that participants will be encouraged to call the study team to discuss details and/or ask questions.

17.4. If user-generated content will be active, how it will be monitored and what actions will be taken to ensure subject safety and study integrity:

N/A

18. Research Related Injury³⁹**18.1. Available compensation in the event of research related injury:**

The study does not involve more than minimal risk to subjects

19. Recruitment Methods⁴⁰**19.1. When, where, and how potential subjects will be recruited:**

On-site recruitment:

Parents/legal guardians checking in for a newborn through 12 month visit will be approached by front desk staff. Those who agree will be approached while waiting for their WCC visit. Clinics will have flyers on display about the study as an additional method for alerting parents to the possibility of being approached by research staff. For those approached in clinic, study staff will explain the study, screen for eligibility, provide the consent form, and obtain consent. When possible, parents/legal guardians will be given the opportunity to discuss the study in a private room.

Off-site recruitment:

- **Method 1: When research staff are limited from recruitment on-site:** clinic sites will be informed of pre-screened visits that are anticipated to be eligible for enrollment. Clinic staff will be able to give parent/legal guardians a copy of the consent form/information sheet prior to research staff contacting them. Parent/legal guardians will have the option to decline a call from research staff. Study staff (who have access to the clinic WCC visit schedule and that have received training to use the clinic's EHR) will call families to explain the study, screen for eligibility, and obtain verbal consent over the phone and document the consent process by entering the date and time in RedCap.
- **Method 2: Under extenuating circumstances, such as the 2019- 2020 SARS-CoV-2 (COVID-19) for the Tacoma, Washington and Los Angeles, California sites:** Clinic staff will ask parent/legal guardians, over the phone during appointment reminder calls, if the research team can contact them to explain the study. Due to the risks associated with COVID-19 transmission, clinic staff are limited in their ability to provide the study information sheet in-person. Parent/legal guardians will have the option to decline a call from research staff. Parent/legal guardians will only be contacted by research staff after clinic staff inform the parent of the study. Under these specific circumstances, the research staff cannot rely on mailing an opt-out letter and information sheets prior to the patients scheduled visit. The research and clinic staff have no other possible alternative to communicating with participants without increasing the risk to parent/legal guardians and their infant children during this fast-evolving public health crisis.
- **Method 3: To increase accrual rates at Community Health Care (Tacoma, WA) study sites:** Study staff will mail an (i) opt-out letter and the study (ii) information sheet to families that have a clinic visit scheduled or due within a 1-month period for routine care. Parents who receive mail communication from the research team will not be added to the pre-screened list that clinic staff inform of the study during their appointment reminder calls. Parent/legal guardians will have the option to decline a call from research staff by replying by call, text, or email. Study staff will call participants about one week after mailings are sent and before the scheduled well-child care visit. The opt-out letter is co-signed by CHC's medical director and the study PI.

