5.4. Data to be collected, including long-term follow-up data:¹¹

Baseline Survey (at enrollment), 6-Month Survey (participant retention survey) and 12-month Survey and Chart review at 12-month post enrollment.

6. Data and Specimen Banking¹²

6.1. Complete list of the data and/or specimens to be included in the bank:¹³

Names and contact information for participants enrolled prior to March 2020. Participant baseline data prior to March 2020.

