10.2. Total number of subjects to be enrolled across all participating sites:³⁰

100 parent/legal guardian-child dyads per each of the 10 clinics. For a total of 1,000.

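### Enrolment and 12-month follow-up straddle March 2020, but section 14.1 prespecifies no calendar-period term, and the explicit Aim 2a covariate rule does not cover one

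*Combined protocol and SAP*

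**What the plan says.** **Timing.** Section 6.1 lists for the COVID survey study "Names and contact information for participants enrolled prior to March 2020", together with their baseline data, so accrual had begun by then. Section 19.1, Method 2, sets out phone recruitment "Under extenuating circumstances, such as the 2019- 2020 SARS-CoV-2 (COVID-19") for both the Tacoma and Los Angeles sites. Section 22.2.2 asks for altered HIPAA authorization so that enrolment can go on during social distancing. Section 8 gives 12 months of participation per family, 12 months of accrual and completion in June 2021.

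**Design.** Section 5.1 describes ten clinics randomised in five pairs, blocked by FQHC, location and size. Section 10.2 sets the same target everywhere: "100 parent/legal guardian-child dyads per each of the 10 clinics". Method 3 in section 19.1 adds a mailing "To increase accrual rates at Community Health Care (Tacoma, WA) study sites".

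**Analysis.** The Aim 1 model in section 14.1 has intervention status, a clinic random effect, baseline covariates and further confounders that are not listed. Aim 2a is to be set up along the lines of Aim 1, but then gives its own covariate rule: "The analysis will be adjusted for any baseline child, parent, or household characteristics that are significantly different between control and intervention groups". Aim 4 follows Aims 1 and 2a. No aim names calendar period, enrolment date or a COVID-19 sensitivity analysis.

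**The concern.** ED visits, well-visit attendance and services received can all change with the calendar period in which a child's 12 months fall. Recruitment, consent, HIPAA and payment sections were adapted to the pandemic; the analysis section was not.

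Two things are at stake. First, if clinics differ in how much of their follow-up falls after March 2020, a period effect becomes extra between-clinic variance, and that is the variance that limits a ten-clinic trial. Second, if the five intervention clinics happen to have a different exposed share from the five control clinics, the realised arm difference shifts. A clinic random effect absorbs the first into the standard error but does not correct the second.

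The explicit Aim 2a rule would not pick this up. Enrolment period is not a child, parent or household characteristic, and a significance filter would in any case drop a prognostic imbalance that missed p < 0.05. Under Aim 1 the term is possible but left to choice after the data are seen.

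**Working it through.** **1. The plan's own figure.** Section 10.4 has 75 evaluable per site and 20% dropout: 75/(1 − 0.20) = 93.75, rounded up to 94, and 94 × 10 = 940. This reproduces.

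**2. Baseline for power.** Section 10.4 gives "Two-sided tests are used with a type I error rate of 0.05", an ICC of 0.01, and the statement that "we will have at least 80% power to detect the intervention effect for both anticipatory guidance and ED visits". The pilot mean, SD and ED rates behind it are not printed; the ED input is described only as "the rates of 2 or more ED visits as observed in our pilot RCT". The 80% cannot be reproduced, so I solved backwards for the effect that gives it:
- design effect = 1 + 74 × 0.01 = 1.74
- n per arm = 5 × 75 = 375; effective n = 375/1.74 = 215.5
- SE of the arm difference = √(2 × 1.74/375) = 0.0963 SD
- effect with 80% power = (1.960 + 0.842) × 0.0963 = 0.270 SD (normal approximation).

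**3. Added between-clinic variance.** Assumptions not in the documents: s = SD across clinics of the share in the later period; δ = period effect in outcome SDs. Then ICC′ = (0.01 + (sδ)²)/(1 + (sδ)²), design effect = 1 + 74 × ICC′, and power = Φ(0.270/√(2 × design effect/375) − 1.96).

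| s | δ | ICC′ | Design effect | Power |
|---|---|---|---|---|
| 0.1 | 0.1 | 0.0101 | 1.75 | 79.8% |
| 0.1 | 0.2 | 0.0104 | 1.77 | 79.3% |
| 0.1 | 0.3 | 0.0109 | 1.81 | 78.5% |
| 0.2 | 0.2 | 0.0116 | 1.86 | 77.4% |
| 0.2 | 0.3 | 0.0136 | 2.00 | 74.3% |
| 0.2 | 0.5 | 0.0198 | 2.47 | 65.3% |

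**4. Shift in the realised difference.** Shift = (arm difference in exposed share) × δ, set against the SE of 0.0963 SD. The type I error is conditional on that imbalance, with the clinic variance taken as known.

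| δ | Arm difference in share | Shift (SD) | Shift as % of 0.270 | Conditional type I error |
|---|---|---|---|---|
| 0.2 | 10 points | 0.02 | 7% | 5.5% |
| 0.2 | 20 points | 0.04 | 15% | 7.0% |
| 0.5 | 5 points | 0.025 | 9% | 5.8% |
| 0.5 | 20 points | 0.10 | 37% | 18.0% |

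Steps 3 and 4 are two views of the same variation, averaged over clinic allocations and conditional on one of them. They should not be added together.

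**5. ED visits.** Assume that the rate of 2 or more visits moves by 3 to 10 points between periods and that the arms differ by 5 to 20 points in exposed share. The spurious difference is then 0.05 × 3 = 0.15 to 0.20 × 10 = 2.0 percentage points. Its SE, √(2p(1 − p) × 1.74/375), is 2.9 points at p = 10% and 3.9 points at p = 20%.

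**6. How exposure varies.** If June 2021 is the end of the last follow-up, accrual runs from June 2019 to June 2020, and families have 3 to 12 months of follow-up after March 2020. If the three-month survey window of section 5.2 is also reserved, accrual runs from March 2019 to March 2020, with 0 to 12 months. A family enrolled in February 2020 has about 11 of 12 months after March 2020, yet a before/after split on enrolment would class it as before.

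**The case against.** The strongest answer is randomisation. Clinics were allocated at the end of 2017, so timing imbalance is zero in expectation. Pairing within FQHC, location and size balances FQHC-level timing if the equal targets are met, and size plausibly drives accrual speed. Chance imbalance is between-clinic variation, which the clinic random effect is there to carry. All of this stands, and it rules out a claim of systematic bias. It does not show that paired clinics recruited in step; an equal target of 100 says nothing about when it is reached.

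A reader might infer three stronger things that the documents do not support:
- **That the plan cannot admit a period term.** Aim 1 leaves room for further confounders and Aim 2a is modelled on Aim 1. The defect is that the term is not prespecified and the two covariate rules do not match.
- **That Method 3 shows an arm imbalance.** It applies to the Tacoma FQHC as a whole, which has two intervention and two control clinics. Method 2 covers both regions.
- **That power drops to 65%.** This needs δ = 0.5. The assumed 3 to 10 point ED change corresponds to only 0.03/√(0.20 × 0.80) = 0.08 to 0.10/√(0.10 × 0.90) = 0.33 SD.

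**Conclusion.** The point holds as a gap in prespecification. Enrolment and follow-up straddle March 2020, no model commits to a period term, and the explicit Aim 2a rule does not reach one. The consequence is conditional: period differences can cost precision and can shift the realised arm difference, but no document shows that they did.

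The size rests wholly on assumed clinic spreads and period effects. For s of 0.1 to 0.2 and δ of 0.1 to 0.3, power falls from 80% to between 79.8% and 74.3%; the 65% figure is an outer case. An arm imbalance of 5 points is nearly harmless even at δ = 0.5, and the largest ED shift in step 5 stays below one SE. All figures use normal theory at the 0.270 SD effect solved for above. Adjustment would recover the loss only so far as one term captures the period effect and that effect is similar across clinics. The change is worth making because it is nearly free, and because a covariate fixed in advance is better than one chosen by significance test or after the data are seen.

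**What to change.** In section 14.1:
- Prespecify the fraction of each child's 12-month window that falls after March 2020 (or enrolment date) as a fixed covariate in every Aim 1, 2a and 4 model, whether or not it differs between arms. Do not use a before/after split on enrolment, for the reason in step 6.
- Align the Aim 2a covariate rule with this, so that a prespecified covariate does not have to pass a significance test to stay in the model.
- Report accrual over time by clinic and arm, so that a reader can see whether paired clinics recruited in step.

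The cost is one sentence of model text and one family-level degree of freedom. The surveys are already timed from the enrolment date, so no new data are needed. Because the covariate varies between families within a clinic, it takes almost nothing from the scarce clinic-level degrees of freedom.
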